7.7.4 Vital Signs

Vital signs, including pulse, systolic blood pressure, diastolic blood pressure, temperature, and respiratory rate will be summarized. Summary statistics of raw data and change from baseline values for each vital signs parameter will be presented by treatment arm and time point. Data will be summarized as appropriate to the variable type. For change from baseline summaries, the results collected at baseline (visit 0) will be used in these calculations or the last data available prior to Visit 0 as per Section 5 definitions. Subjects with an undefined change from baseline, because of missing baseline data, will be excluded. Shift tables will be presented for each vital sign parameter with counts and percentages of subjects, by treatment arm and time point, for shift (change) from baseline, using the normal ranges for vital signs parameters. Normal ranges for vital signs data are defined in Appendix 2.

Vital signs data from unscheduled visits will be listed but will not be included in any summaries.

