Investigational Therapy:	
d-Amphetamine Transdermal Drug Delivery System (d-ATS) 9-hour patch (5 mg d-amphetamine /4.76 cm^2 patch).
 
d-Amphetamine Transdermal Drug Delivery System (d-ATS) 9-hour patch (10 mg d-amphetamine /9.52 cm^2 patch).
 
d-Amphetamine Transdermal Drug Delivery System (d-ATS) 9-hour patch (15 mg d-amphetamine /14.29 cm^2 patch).
 
d-Amphetamine Transdermal Drug Delivery System (d-ATS) 9-hour patch

Amendment 4: Version 5.0 May-08-2013

Amendment 3: Version 4.0 December-11-2012

Amendment 2: Version 3.0 October-31-2012

Amendment 1: Version 2.0 August-02-2012

Final Protocol May-25-2012

	(20 mg d-amphetamine /19.05 cm  patch).
Reference Therapy:	Placebo
Treatment Duration:	5 weeks of dose titration period and 2 weeks of double blind treatment period
Efficacy Assessments	
ADHD-RS-IV at Visit 0 (baseline; Day 0), Visit 1 (Day 7), Visit 2 (Day 14), Visit 3 (Day 21), Visit 4 (Day 28), Visit 5 (Day 35), Visit 6 (Day 42) and Visit 7 (Day 49).
 
SKAMP and PERMP will be collected as follows:
 
 
Visit -1 (Screening): Level finding math test and 1 PERMP at demonstrated level.
 
Visit 0 (baseline; Day 0): Two practice PERMPs at demonstrated level
 
Visit 1(Day 7), Visit 2 (Day 14), Visit 3 (Day 21) and Visit 4 (Day 28): One practice PERMP at demonstrated level
 
Visit 5 (Day 35): Half day practice classroom;(SKAMP and PERMP pre-dose and 1 and 2 hours post dose)
 
Visit 6 (Day 42) and Visit 7 (Day 49): PERMP and SKAMP within 30 minutes prior to dosing and at 1, 2, 3, 4.5 (4½), 6, 7, 9, 10, and 12 hours following administration of study drug.
 
Conners' Parent Rating Scale-Revised Short Form will be completed by parent/caregiver on the day before a clinic visit: on Day 6, Day 13, Day 20, Day 27, Day 34, Day 41, and Day 48.
 
Clinical Global Impression: CGI-S will be collected on Day 0 (pre-dose). CGI-I will be collected on Visit 1(Day 7), Visit 2 (Day 14), Visit 3 (Day 21), Visit 4 (Day 28), Visit 5 (Day 35), Visit 6 (Day 42) and Visit 7 (Day 49).
 

Safety Assessments ECG	
ECG assessments will be performed as follows:
 
 
Visit -1 (Screening)
 
Visit 0 (baseline; Day 0)
 
Visit 5 (Day 35), Visit 6 (Day 42), and Visit 7 (Day 49) or early termination (prior to discharge).
 

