Vital Signs	
Vital sign assessments will be performed at:
 
 
Visit -1 (Screening)
 
Visit 0 (baseline; Day 0)
 
Visit 1(Day 7), Visit 2 (Day 14), Visit 3 (Day 21), Visit 4 (Day 28), and Visit 5 (Day 35)
 

Amendment 4: Version 5.0 May-08-2013

Amendment 3: Version 4.0 December-11-2012

Amendment 2: Version 3.0 October-31-2012

Amendment 1: Version 2.0 August-02-2012

Final Protocol May-25-2012

	
 
Visit 6 (Day 42) and Visit 7 (Day 49): 30 minutes pre-dose and 4 hours and 12 hours post dose or early termination.
 

Suicidality	
C-SSRS will be administered as follows:
 
 
Visit 0 (baseline; Day 0)
 
Visit 1(Day 7, Visit 2 (Day 14, Visit 3 (Day 21, Visit 4 (Day 28, Visit 5 (Day 35, Visit 6 (Day 42, and Visit 7 (Day 49) or early termination: prior to discharge.
 

Laboratory Evaluations	
Blood and urine samples for clinical laboratory evaluations will be collected at:
 
 
Visit -1 (Screening)
 
Prior to discharge on Visit 7 (Day 49) or early termination
 

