### **6.9 Vital Signs**

Vital sign measurements will consist of oral body temperature, sitting respiratory rate, and sitting systolic and diastolic blood pressure, and sitting pulse after a minimum of 5 minutes rest.

Blood pressure (BP) should be determined by cuff (manual or automated is acceptable; however the same method should be used throughout the study). A BP cuff suitable to the subject's arm should be used for all BP measurements. All BP measurements should be taken from the same arm and whenever possible, performed by the same site personnel throughout the study.

Amendment 4: Version 5.0 May-08-2013

Amendment 3: Version 4.0 December-11-2012

Amendment 2: Version 3.0 October-31-2012

Amendment 1: Version 2.0 August-02-2012

Final Protocol May-25-2012

Vital signs will be evaluated to determine whether the values are: 1) Normal; 2) Abnormal, Not Clinically Significant and 3) Abnormal, Clinically Significant. Clinically significant values should be recorded as AEs and will be followed to resolution or up to 30 days following patch removal, whichever comes first.

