### **6.12 Electrocardiogram**

A standard 12-lead ECG should be obtained after the subject has been in a supine position for at least 5 minutes. ECGs will be recorded using a standard cardiograph on standard ECG paper.

Any ECG which demonstrates a clinically significant abnormality during the study will be repeated within 24 hours. If the abnormality persists, ECGs will be obtained daily until the changes have resolved or are satisfactorily explained. ECGs will be interpreted by a qualified physician and evaluated to determine whether the ECG findings are: 1) Normal; 2) Abnormal, Not Clinically Significant and 3) Abnormal, Clinically Significant. Clinically significant ECG findings should be recorded as AEs and will be followed to resolution or up to 30 days following patch removal, whichever comes first.

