7.7.6 Physical Examinations, ECGs, and Other Observations Related to Safety

There will be no separate physical examination listings since screening physical examination abnormalities were recorded as Medical History and post-randomization physical examination abnormalities were recorded as AEs.

All quantitative 12-lead ECG interval measurements (QRS, QT, QTc, etc.) will be summarized with descriptive statistics by visit, and treatment arm. Summary statistics of raw data and change from baseline values will be presented by treatment arm and time point. Data will be summarized as appropriate to the variable type. For change from baseline summaries, subjects with an undefined change from baseline, because of missing baseline data, will be excluded.

ECG assessments at each study visit will be evaluated to determine whether the ECG findings are: 1) Normal; 2) Abnormal, Not Clinically Significant and 3) Abnormal, Clinically Significant. Descriptive statistics (numbers and percentages of subjects in each of the three categories) will be presented by treatment arms for each visit. In addition shift tables will be also presented based on the above three categories of ECG interpretations, by treatment arm and time point.

ECG data from unscheduled visits will be listed but will not be included in any summaries.

Screening results from the Wechsler Abbreviated Scale of Intelligence - Second Edition (WASI-II) and M.I.N.I. International Neuropsychiatric Interview (M.I.N.I. 6.0) are used as to assess inclusion/exclusion criteria and are not recorded. These data will not be listed or included in any summaries.

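### The described vital-sign tables bound, but do not give, the number of children ever out of range in a study period, and unscheduled readings enter no summary

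*SAP*

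**What the plan says.** SAP 7.7.4 plans summary statistics for each vital sign by arm and time point, and shift tables giving "counts and percentages of subjects, by treatment arm and time point, for shift (change) from baseline, using the normal ranges for vital signs parameters". The normal ranges are in SAP Appendix 2. The section ends by saying that "Vital signs data from unscheduled visits will be listed but will not be included in any summaries". Protocol 8.4.3 has the same layout and the same exclusion.

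Protocol 6.9 supplies a second route into the tables: "Clinically significant values should be recorded as AEs". SAP 7.7.1 counts a child once per adverse-event category and keeps the two study periods separate.

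The protocol synopsis schedules vital signs at Visits 1 to 5 during dose optimization. On each classroom day (Visits 6 and 7) they are taken "30 minutes pre-dose and 4 hours and 12 hours post dose or early termination". SAP section 7 pools Visits 6 and 7 by treatment and maps early-termination readings to the next scheduled visit.

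For ECGs, SAP 7.7.6 says that "shift tables will be also presented based on the above three categories of ECG interpretations, by treatment arm and time point" and that "ECG data from unscheduled visits will be listed but will not be included in any summaries".

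**The concern.** Safety is a primary objective (Protocol section 4), the drug is a sympathomimetic, and the subjects are children whose dose is stepped up at weekly visits. A natural safety question is how many children went out of range at any time during titration, or during a week on d-ATS compared with a week on placebo. A set of by-visit rows leaves that open: 5% at every visit may be the same few children throughout or a different few each time, and those are different safety findings.

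The exclusion of unscheduled readings adds a second gap. A recheck between visits that is out of range reaches a table only if the investigator calls it clinically significant, because it is then recorded as an adverse event.

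**Working it through.** The plan states no figure on this point, so there is none to reproduce. The check is which counts the described tables yield, and how far they leave the per-child number open.

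**Readings per child (protocol synopsis)**
- Dose optimization: Visits 1 to 5, so k = 5.
- Double-blind week: pre-dose, 4 h and 12 h on one classroom day, so k = 3. The pre-dose reading belongs in the count because it follows six days of that week's patches, and SAP 7.7.4 takes baseline from Visit 0.
- ECG: "Visit 5 (Day 35), Visit 6 (Day 42), and Visit 7 (Day 49) or early termination (prior to discharge". That is one scheduled on-study ECG in dose optimization and one per double-blind treatment, so k = 1.

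**Formulas.** If each reading is out of range at rate p and none is missing, the share of children ever out of range is:
- at least p (the same children each time);
- at most min(1, k × p) (different children each time);
- 1 − (1 − p)^k if readings are independent;
- as a middle case, 1 − ∫ φ(u) Φ((z − √0.5·u)/√0.5)^k du with z = Φ⁻¹(1 − p), which is a latent-normal correlation of 0.5.

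**Results.** The rates and the correlation are assumptions; the documents give neither.

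| k | assumed p | lowest | correlation 0.5 | independent | highest |
|---|---|---|---|---|---|
| 5 | 5% | 5% | 16.6% | 1 − 0.95^5 = 22.6% | 5 × 5% = 25% |
| 5 | 10% | 10% | 29.2% | 1 − 0.90^5 = 41.0% | 5 × 10% = 50% |
| 3 | 5% | 5% | 11.8% | 1 − 0.95^3 = 14.3% | 3 × 5% = 15% |
| 3 | 10% | 10% | 21.8% | 1 − 0.90^3 = 27.1% | 3 × 10% = 30% |

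In children: suppose about 90 are randomized and 9 are out of range at each of the three classroom readings on one treatment. Then the number ever out of range is anywhere from 9 to 3 × 9 = 27.

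**ECG.** With k = 1 the lowest and highest values are both p. The by-visit table already gives the per-child count of abnormal scheduled ECGs within a period.

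**Unscheduled vital signs.** If judged clinically significant, the value is recorded as an adverse event and is counted once per child per period. If not, SAP 7.7.4 sends it to listings only. The documents do not say how many such readings to expect, so this part has no size.

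**The case against.** The strongest reply is that this is a preference. The by-time-point tables are correct for what they claim, the protocol and SAP agree, safety is descriptive with no inferential tests, and no stated claim rests on an ever-out-of-range count. Clinically significant values reach the adverse-event tables. All data are listed by subject, so with about 90 randomized children a reader could count by hand. All of that stands, and it makes this an improvement rather than the correction of an error. It does not put the per-child number into any described table, and the listings leave the reader to derive it.

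SAP Appendix 2 and the table shells were not supplied, so a per-child layout may exist there. That is why the point is confined to the supplied text. A shell would still not override the explicit exclusion of unscheduled readings from summaries.

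A reader might infer that the omission can only make the number of affected children look too small. The documents do not support that: a reader who takes one row may undercount, but one who adds rows may overcount. A reader might also infer an equal gap for ECGs. There is almost none. One ECG is scheduled per period, and the repeats that Protocol 6.12 requires follow findings that already count as adverse events: "Any ECG which demonstrates a clinically significant abnormality during the study will be repeated within 24 hours".

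Two objections concern the remedy and are right. A worst value needs a direction, since a vital sign can leave its range high or low. And if children are rechecked more often on one treatment, including unscheduled readings gives that treatment more chances to be counted. The fix handles both.

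**Conclusion.** The point holds for vital signs, as a cheap improvement to the reporting of a primary objective. The tables described in the supplied text bound the number of children ever out of range over a period without giving it. At an assumed 5% per reading the bounds are 5% to 25% over dose optimization and 5% to 15% over a double-blind week; at an assumed 10% they are 10% to 50% and 10% to 30%. The width follows from the number of readings. The levels rest on assumed rates, held constant across visits, and a constant rate is a simplification under stepwise titration. The loss from excluding unscheduled readings is real in kind but cannot be sized. The by-time-point tables are not wrong and should stay.

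**What to change.** In SAP 7.7.4 and Protocol 8.4.3, limit the sentence excluding unscheduled readings to the by-time-point tables. Then add, for each vital sign, a shift table from the Visit 0 baseline to each child's highest post-baseline value and, separately, to the lowest, using the Appendix 2 ranges.

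- **Dose optimization:** all subjects combined.
- **Double-blind period:** by the treatment received that week.
- **Readings counted:** all on-treatment readings in the period. On the classroom day these are pre-dose, 4 h and 12 h; early-termination and unscheduled readings are added.
- **Unequal rechecking:** give the double-blind count with and without unscheduled readings, and show the number of readings per child by treatment.

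The cost is a wording change and a few extra descriptive tables from data already collected, with no new assessments and no tests. The drawback is that the count rises with the number of readings and does not show timing. The by-time-point tables cover timing, and the number of readings per child lets the count be read in context.

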7.7.5 Columbia Suicide Severity Rating Scale (Children's Version)

Summaries will be presented for each of the subscales (i.e. Suicidal Ideation and Suicidal Behavior).

Suicidal Ideation will be summarized for each of the following 5 ideation categories:

1. Wish to be dead
2. Non-specific active thoughts
3. Active suicidal ideation with any methods (not plan) without intent to act
4. Active suicidal ideation with some intent to act, without specific plan
5. Active suicidal ideation with specific plan and intent.

Descriptive summary of the number and percentages of subjects with the responses of “Yes” for each of the five categories will be presented by treatment arms and visit. The intensity and frequency for ideation will also be summarized descriptively by treatment arm and visit.

Suicidal Behavior will be summarized for each of the following 5 behavior categories:

1. Actual attempt
2. Interrupted intent
3. Aborted attempt
4. Preparatory Acts or Behavior
5. Suicidal behavior present during assessment period.

Descriptive summary of the number and percentages of subjects with the responses of “Yes” for each of the five categories will be presented by treatment arms and visit.

Additionally, the number of subjects who reported at least one occurrence of suicidal ideation and at least one occurrence of suicidal behavior, and subjects who reported at least one occurrence of suicidal ideation or at least one occurrence of suicidal behavior will be summarized by treatment arm and visit. For these summaries a subject will only be counted once in each in each sub-category.

7.7.6 Physical Examinations, ECGs, and Other Observations Related to Safety

There will be no separate physical examination listings since screening physical examination abnormalities were recorded as Medical History and post-randomization physical examination abnormalities were recorded as AEs.

All quantitative 12-lead ECG interval measurements (QRS, QT, QTc, etc.) will be summarized with descriptive statistics by visit, and treatment arm. Summary statistics of raw data and change from baseline values will be presented by treatment arm and time point. Data will be summarized as appropriate to the variable type. For change from baseline summaries, subjects with an undefined change from baseline, because of missing baseline data, will be excluded.

ECG assessments at each study visit will be evaluated to determine whether the ECG findings are: 1) Normal; 2) Abnormal, Not Clinically Significant and 3) Abnormal, Clinically Significant. Descriptive statistics (numbers and percentages of subjects in each of the three categories) will be presented by treatment arms for each visit. In addition shift tables will be also presented based on the above three categories of ECG interpretations, by treatment arm and time point.

ECG data from unscheduled visits will be listed but will not be included in any summaries.

Screening results from the Wechsler Abbreviated Scale of Intelligence - Second Edition (WASI-II) and M.I.N.I. International Neuropsychiatric Interview (M.I.N.I. 6.0) are used as to assess inclusion/exclusion criteria and are not recorded. These data will not be listed or included in any summaries.

8. INTERIM ANALYSES

No interim analysis is planned for this study.

9. DATA REVIEW

Final data for analysis will be cleaned prior to receipt for statistical programming. The purpose of this section is to indicate the history of the data and the process used to ensure that the data are acceptable for statistical analysis prior to database lock.

9.1 DATA HANDLING AND TRANSFER

All of the data will come from the █ data management group in SAS® dataset format (SAS version 9.1 or later). Coexistent diseases and AEs will be coded using the Medical Dictionary for Regulatory Activities (MedDRA), version 15.0 or later, to assign a system organ class (SOC) and preferred term (PT) to each AE. Prior and concomitant medications will be coded to preferred drug names using the latest available World Health Organization Drug Dictionary (WHODD).

More details about the data handling can be found in the Data Management Plan.

9.2 DATA SCREENING

Beyond the data screening built into the Data Management Plan, the programming of analysis datasets, tables, figures, and listings (TFL) provides additional data screening. Presumed data issues will be output into SAS logs identified by the word “Problem” and extracted from the logs by a SAS macro and sent to Data Management.

Prior to database lock and unblinding, the database will be frozen for a period of time during which no changes will be made to the database. A review of pre-freeze TFLs run on clean subjects and post-freeze, blinded TFLs run on the frozen database allow for further data screening prior to lock. The post-freeze blinded TFLs will be discussed with the sponsor in a data review meeting to identify any final data issues and seek corrections prior to database lock. The █ statistician and the sponsor must approve database lock.

10. VALIDATION

█ goal is to ensure that each TFL delivery is submitted to the highest level of quality. Quality control procedures will be documented separately in the study-specific quality control plan. The following describes the procedure typically followed at █.

Derived datasets will be independently reprogrammed by a second programmer and the separate datasets produced must match 100%.

Tables will be independently reprogrammed by a second programmer for numeric results. Statisticians will be involved in the process of programming and validating tables that include inferential statistical results.

Figures will be checked for consistency against corresponding tables and listings, or independently reprogrammed if there are no corresponding tables or listings.

Listings will be checked for consistency against corresponding tables, figures, and derived datasets.

The entire set of TFLs will be checked for completeness and consistency prior to its delivery to the client by the lead analysis programmer, the lead statistician, and a senior level statistician, or above, who is not a member of the project team.

The validation process will be repeated any time TFLs are redelivered using different data. Execution of this validation process will be documented through the study Table of Programs which is provided to the client at study conclusion.

APPENDIX 1 GLOSSARY OF ABBREVIATIONS

Glossary of Abbreviations:	
ADHD	Attention Deficit Hyperactivity Disorder
ADHD-RS-IV	Attention-Deficit/Hyperactivity Disorder Rating Scale, Version IV
AE	Adverse Event
ATC	Anatomic Therapeutic Classification
BMI	Body Mass Index
C-SSRS	Columbia Suicide Severity Rating Scale
CGI	Clinical Global Impression
CGI-I	Clinical Global Impression-Improvement
CGI-S	Clinical Global Impression-Severity
CI	Confidence Interval
CPRS-R:S	Conners' Parent Rating Scale-Revised Short Form
CRF	Case Report Form
C-SSRS	Columbia Suicide Severity Rating Scale
CSR	Clinical Study Report
d-ATS	d-Amphetamine Transdermal Drug Delivery System
DSM-IV-TR	Diagnostic and Statistical Manual of Mental Disorder, Fourth Edition, Text Revision
ECG	Electrocardiogram
eCRF	Electronic Case Report Form
FAS	Full analysis set
ICH	International Conference on Harmonization
ITT	Intent-To-Treat
IVRS	Interactive Voice Response System
LOCF	Last Observation carried Forward
LS	Least squares
MAR	Missing at random
MCAR	Missing completely at random
MedDRA	Medical Dictionary for Regulatory Activities
MNAR	Missing not at random
NRS-11	Numeric Rating Scale (11 point scale)
PDV	Protocol Deviation or Violation
PERMP	Permanent Product Measure of Performance
PERMP-A	Permanent Product Measure of Performance , Number of Problems Attempted

Glossary of Abbreviations:	
PERMP-C	Permanent Product Measure of Performance , Number of Problems Correct
PT	Preferred term
SA	Safety
SAP	Statistical Analysis Plan
SAE	Serious Adverse Event
SD	Standard Deviation
SKAMP	Swanson, Kotkin, Agler, M-Flynn and Pelham Scale
SOC	System Organ Class
TEAE	Treatment-Emergent Adverse Event
TFL	Tables, Figures, and Listings
VAS	Visual Analog Scale
WASI-II	Wechsler Abbreviated Scale of Intelligence - Second Edition
WBS	Wong Baker Faces Scale
WHODD	World Health Organization Drug Dictionary
